4. STUDY TREATMENT & DESIGN

Study design: This is an open label, proof of concept single site study and will be conducted at the Department of Dermatology, URMC

- Screening visit (-28 days before start of treatment)
- visit 1 - (V1, day 0), start of active treatment;
- visit 2 – 28 +/- 3 days (4 weeks) treatment;
- visit 3 – 56 +/- 3 days (8 weeks) treatment;
- visit 4 – 84 +/- 3 days (12 weeks) end of treatment
- visit 5 – 112 +/- 3 days (16 weeks) safety follow up 4 weeks post treatment
- during each visit a skin swab will be collected and stored in the lab for future microbiology study
- Skin Symptom questionnaire will be done during each visit.

Screening visit (-28 days)

- 1) Consenting and confirmation of inclusion & exclusion criteria
- 2) Medical history
- 3) Physical exam with focus on skin exam
- 4) Collection of concomitant medications
- 5) Fasting blood draw for safety labs (CBC with diff, Chemistry, Lipid panel)
- 6) Urinalysis
- 7) Possible washout period

- 8) Possible schedule PATCH test if investigator believes clinically necessary to r/o contact dermatitis
- 9) Urine Pregnancy test for woman of childbearing potential
- 10) Scheduling visit 1

Visit 1 (Day 0):

- 1) Confirmation of inclusion & exclusion criteria
- 2) General history
- 3) Physical exam
- 4) Review of concomitant medications
- 5) Urine pregnancy test for woman of childbearing potential at each visit. Counseling on acceptable birth control measures to use throughout treatment period including 30 days after stopping study drug (16 weeks or 112 days)
- 6) Clinical scores for chronic hand dermatitis
- 7) Itch and other QoL assessments; review daily diary
- 8) Digital pictures of the target area/hands
- 9) Non-invasive skin barrier Measurements: TransEpidermal Water Loss (TEWL) and optional pH may also be performed
- 10) Repeated tape stripping (Cuderm™ tape) of peri-lesional (0, 5, 10, 15, 20 tape) locations from treated area will be collected as part of the TEWL assessment and to assess for SC cohesion/integrity (rate of change in TEWL with repeated stripping). Serial measurements of TEWL will be performed after tape stripping as previously described^{vii}. This will also allow collecting proteins (eluted from the tape) for validation of biomarkers
- 11) Dispense Investigational drug for 4 weeks
- 12) Provide instructions to complete at home diary.
- 13) Provide date of Visit 2
- 14) Weight of the tube to check for subject's compliance
- 15) Skin swabs (optional)
- 16) Skin symptom questionnaire (optional)

Visit 2 (Day 28 +/-3) and Visit 3 (Day 56 +/-3) and Visit 4 (Day 84 +/-3):

- 1) Review subject diary and address any questions, concerns, or missed doses
- 2) Review of concomitant medications
- 3) Adverse events assessment
- 4) Questionnaire to clinically characterize CHD
- 5) Urine Pregnancy test for woman of childbearing potential.
- 6) Clinical score for CHD
- 7) Itch and other QoL assessments, review daily diary

- 8) Digital pictures of the targeted area
- 9) Non-invasive skin barrier Measurements: transepidermal water loss. Optional: pH
- 10)Repeated tape stripping (Cuderm™ tape)
- 11)Dispense investigational drug for following 4 weeks (except Visit 4, end of treatment)
- 12)Review Diary instructions
- 13)Weight of the tube to check for subject's compliance
- 14)Provide date for next visit
- 15)Skin swabs (optional)
- 16)Skin symptom questionnaire (optional)

Visit 5 (Day 112 +/-3):

- 1) Review subject diary and address any questions, concerns, or missed doses
- 2) Review concomitant medications
- 3) Adverse Events Assessment
- 4) Questionnaire to clinically characterize CHD
- 5) Urine Pregnancy test for woman of childbearing potential.
- 6) Clinical score for CHD
- 7) Itch and other QoL assessments; review daily diary
- 8) Digital pictures of the targeted area
- 9) Non-invasive skin barrier Measurements: transepidermal water loss. Optional: pH and skin swab
- 10)Repeated tape stripping (Cuderm™ tape)
- 11)Weigh returned tubes

Unscheduled Visit(s)

Any follow-up assessment that is performed to monitor a subject will be collected as an unscheduled visit. The study team is responsible for review of any side effects, concomitant medications, and a brief physical examination. The remaining elements of the unscheduled visit are up to the discretion of the investigator and may include any of the events listed in Visits 1 through Visit 5.

Study procedures & methods

- **Disease status assessment:** **1)** Investigator Global Assessment (IGA), which will provide information of the overall disease (5-point scale: clear, almost clear, mild, moderate, severe) and it is the score requested by FDA for clinical study. Data will be reported as and **2)** Hand Eczema Severity Index (HECSI)^{viii}, a well-accepted and validated scoring system for disease activity. It incorporates both the extent and the intensity of the disease. Each hand is divided into five areas: fingertips, fingers (except the tips), palms, back of hands and wrists. Each area will be score for

extension and intensity of the six following clinical signs: erythema, induration/papulation, vesicles, fissuring, scaling and edema; which are graded on the following scale: 0, no skin changes; 1, mild disease; 2, moderate and 3, severe (see appendix). Data will be reported as percent change in HECSI score from baseline to week 4, 8 and 12.

The presence or absence of skin irritation (e.g. macular/papular eruption), redness, atrophy and telangiectasia will be noted at each study visit.

- The **pruritus** intensity will be assessed using Itch Numerical Rating Scale (NRS; see appendix). Data will be reported as proportion of participants with a ≥ 2 and 4-point improvement in Itch Numerical Rating Scale (NRS) score from baseline to week 4, 8 and 12. The NRS comprised of one item and represents the numbers 0 ("no itch") to 10 ("worst imaginable itch"). Subjects are asked to rate the intensity of their itch using this scale. The **Dermatology Life Quality Index (DLQI)** measured 6 disease-specific domains (symptoms and feelings, leisure, daily activities, work and school, personal relationships, and treatment) during the last week; individual items were summed to generate an overall score. Data will be reported as change from baseline to week 12 in DLQI. The **Work Productivity and Activity Impairment-Chronic Hand Dermatitis (WPAI-CHD)** questionnaire elicited the number of work hours missed, hours worked, and impairment while working/performing usual daily activities as a result of chronic hand dermatitis during the past 7 days. The sum of work time missed and work impairment while working yielded the overall work impairment measure. All scores were expressed as percentages, with higher scores indicating greater impairment^{ix}. Data will be reported as change from baseline to week 12 in work productivity and activity impairment index. Will also collect Skin Symptom Questionnaire routinely used by the URMC dermatology department
- **Digital pictures:** A digital picture will be taken with a dedicated digital camera using the Haiku App. The pictures will be labeled with the subject's study ID and date. Pictures will not include identifying information (e.g. facial features, tattoo, etc). Pictures will be taken at a distance for easy identification of the anatomical area and closer to better capture clinical changes. Digital photographs will be used to record the location and monitor the size of target lesions.
- **Venous blood sample:** blood will be obtained for safety lab
- **Skin barrier measurements:** Transepidermal water loss/TEWL, +/- pH will be obtained on treatment area at a perilesional site. This measurement asses the dryness and health of the skin. For each of the specific measurements, a probe will be gently applied on the skin surface for up to 1 minute. We will perform all measurements in a climate-controlled examination room with consistent temperature (~23°C) and humidity (~50%). The patient must be very comfortable in the room in which they are being tested to ensure that perspiration due to stress

or acclimatization does not alter the TEWL. TEWL will be assessed using a non-invasive skin probe that measures skin hydration - or other similar device available in the CTU. The URMC department of Dermatology owns the devices and has experience with measurements. **Stratum Corneum (SC) integrity:** the most superficial layers of the skin will be collected by tape stripping using D-squame (D-squame®, CuDerm, Dallas TX, USA). This is a well-established method used in clinical research to gently perturb the skin barrier. The first tape will be discarded to eliminate dirt and remnants of skin products. Each tape will be gently pressed against the skin with standardized pressure for 5-10 seconds (sec) using a standardized pressurizer (D500–D-squame® pressure instrument, CuDerm)). All subjects will have 20consecutive tapes collected from lesional skin as part of this study. TEWL will be measured after each set of 5 tape strippings. These measurements should provide data to determine if the treatment has an effect on skin barrier integrity. Dsquame tapes will be collected and stored in -80 C freezer (see below). Expression of relevant biomarkers can be investigated using RNA or protein eluted from the tapes. [name] lab is familiar with the methods and analysis

- **Skin swab:** will be collected at each visit. Briefly a sterile swab will be rolled on the dorsal hand (non-dominant hand) at each visit and stored at -80C for future analysis
- **Study Drug Diary:** subjects will be provided with a prepopulated dated calendar to record their twice daily (AM and PM) application of study medication as well as the time the medication is applied. Also, on this diary the subject can indicate if a missed dose occurred and there is a blank space they can write in the reason it was missed. At the END of each day the subject will need to indicate on the same study diary their level of hand dermatitis itch throughout the day – 0=no itch and 10=worst imaginable itch. Subjects will indicate their level 0-10 by circling the number that best applies to them for that particular date. Detailed instructions are provided on the Incyte Study Diary as well as contact information of coordinator.

Prohibited Medications and procedures: use of topical or systemic immunosuppression/immunomodulators medications and Phototherapy is not permitted during the study. Hand surgery or other procedures (including but not limited to Cryotherapy, ED&C, skin biopsy) are disallowed during the study. If medically necessary, the investigator will withdraw the patients from the study.

5. RISK, BENEFITS and PROTECTION AGAINST RISKS

Risks Associated with Digital Picture

There are no known risks for the digital picture. The image will not include identifying features and will be labeled with study subject ID and date. ~~Pictures will be taken with a dedicated camera, stored on a secure server.~~ Pictures will be taken through the Haiku App and stored in the patients EMR in Epic.

Risks Associated with Barrier Assessments

There are no known risks for the barrier assessments.

Risks Associated with Tape Stripping

The risks associated with tape stripping, theoretically, include the rare possibility of an allergic reaction to the tape and infection. Since the tape is removed immediately after application, the risk of reaction is extremely low. In previous and ongoing studies involving tape stripping, it has been noted that a very mild erythema may develop immediately after a series of tape stripplings on one localized area of skin, presumably due to the mild mechanical disturbance. The erythema is expected to resolve within 12 hours without sequelae. The risk of skin infection is extremely low since only superficial skin layers are removed. Subjects will be provided with wound care information and a department phone number to contact should they have any concerns.

Risks of Phlebotomy

The risks of having blood drawn include some pain when the needle goes in, and a small risk of bruising and/or infection at that site. Some people will get lightheaded, nauseous, or faint. Approximately 3 teaspoons of blood will be drawn and is not likely to cause lightheadedness, however subjects will be observed after blood draw to be sure they are comfortable with ambulation. Subjects will be encouraged to drink plenty of water prior to the blood draw. Phlebotomy will be performed at the antecubital fossa to minimize pain and bruising. Subjects will be seated during the blood draw to minimize dizziness and any risk of falling. Pressure will be applied to the site after the draw and a band-aid will be applied to minimize the risk of bleeding and infection. Fasting laboratories will be processed at URMC local lab. We require fasting laboratories as the lipid panel can be influenced by food intake and it is routine care to do fasting laboratories of at least 6 hours. Due to known side effects of systemic class of medication we want to screen patients for leucopenia, high lipids, liver or kidney diseases; normal or non-clinical significant labs at baseline are useful to rule out these problems and can be helpful in case we have side effects during the study.

The clinical trial team will receive and review the laboratory results between 24-48 hours.

Risks of Ruxolitinib 1.5% cream

Skin-related side effects of ruxolitinib cream are rare, but have included local irritation, pain, itch, redness, acne, and rash. While other side effects are not expected and have not been seen in other studies of ruxolitinib cream, there is a potential risk of side effects

that have been observed with much higher doses of ruxolitinib when given by mouth. These risks include infection, low blood counts, liver inflammation, elevated cholesterol, dizziness, headache, fatigue, insomnia, diarrhea, and abdominal pain. As with any treatment, there is a small risk of an allergic reaction, though this has not been documented for ruxolitinib cream.

There is a risk of no change or worsening of disease, as would be true with any change in treatment.

FDA approved medication label information, risks include:

- Patients treated with oral JAK inhibitors for inflammatory conditions are at risk for developing serious infections that may lead to hospitalization or death
- Reported infections include:
 - Active tuberculosis (TB), which may present with pulmonary or extrapulmonary disease
 - Invasive fungal infections (eg, candidiasis, pneumocystosis)
 - Bacterial, viral, and other infections due to opportunistic pathogens
- Avoid use in patients with an active, serious infection, including localized infections
- If a serious infection develops, interrupt therapy until infection is controlled
- Do not resume until the infection is controlled.
- Carefully consider the risks and benefits of treatment before initiating therapy in patients with chronic or recurrent infection
- Closely monitor for developing signs and symptoms of infection during and after treatment

Reproductive Risks

Women of childbearing potential will be counseled to use acceptable birth control methods. Women will not be allowed to participate in this study if they are pregnant, become pregnant, or are nursing an infant.

General Risks

When participating in any research study there is a possibility for invasion of privacy or breach of confidentiality. As with any research study, there may be additional risks that are unknown or unexpected. The subjects are advised to contact their study team with any questions and/or concerns. At that time the study team will determine whether or not any untoward medical occurrence is associated with the study and/or study drug and will be recorded on the Medical History and/or Adverse Event page of the source document.

Adverse Event Reporting

An adverse event (AE) is any observation whether or not considered to be product related, that is unfavorable and unintended and that occurs after any use of an investigational medicinal product.

Any observation of abnormality will be documented on the Adverse event form. The Investigator will document the date of occurrence, severity, resolution, and will assess the relationship of the adverse event to the study drug by assigning a causality assessment. Results from laboratory evaluations which are outside of the laboratory reference range will constitute an adverse event only if the Investigator determines that the result is clinically significant.

Severity will be assessed by the following system:

- Mild: easily tolerated, causing minimal discomfort
- Moderate: sufficiently discomforting to interfere with every day activities
- Severe: prevents normal every day activities

Serious Adverse Events (SAE)

FDA definition: A serious adverse event results in death, is life-threatening, requires inpatient hospitalization or prolongation of existing hospitalization, results in persistent or significant disability / incapacity, results in a congenital anomaly / birth defect. Events fitting these descriptions will be considered adverse events if they occur after treatment with the study drug.

As soon as reasonably possible, subjects will contact the Investigator to report any unfavorable events. The Investigator will assess the case, determine the need for treatment, and consult with Incyte, Inc, particularly in the occurrence of:

- A serious adverse event.
- An unusual frequency of non-serious adverse events.
- Death, even if this does not appear to be related to therapy with the study drug.

The Investigator will notify the URMC Institutional Review Board within approximately 3 working days if a serious adverse event occurs.

SAE Reporting to Incyte

The Principal Investigator (PI) must report all Serious Adverse Events (SAEs) to Incyte within 24 hours of learning of an event, regardless of the PI's causality assessment. This notification should be provided on a completed Serious Adverse Event (SAE) form. SAE reporting for each subject begins the day the informed consent is signed by the patient and within 30 days after subject has completed or discontinued from the study or has taken last dose of the study drug, or as described in the protocol.

SAEs, occurring using Incyte study drug, are reported in accordance with the effective protocol. SAEs occurring with any other commercial drug are reported to the manufacturer of that drug in accordance with regulations and protocol.

Initial SAEs and/or subsequent follow-up reports should be reported via email to [contact] or fax [name]. SAE reports should be for a single subject. SAE forms should be sent with a cover sheet and any additional attachments.

All adverse event information is reported to Incyte on the Principal Investigator's/Institution's Adverse Event Report Form, or a CIOMS-I or MedWatch Form FDA 3500A, or on an Adverse Event Report Form which may be provided by Incyte upon request. The Principal Investigator does not provide medical records (e.g., discharge summary) to Incyte, unless specifically requested.

Reporting of Pregnancy to Incyte an "Initial Pregnancy Report" or equivalent must be completed in full and emailed to [contact] or faxed to [name] within 24 hours of discovery of a pregnancy of a subject who has taken the Incyte product or the pregnancy of a partner for a subject who has taken the Incyte product. The "Follow-up Pregnancy Report Form" or equivalent must be completed and emailed to [contact] or faxed to [name] within 30 days after delivery, so that Incyte is provided with information regarding the outcome of the pregnancy. If the pregnancy results in any events that meet the serious criteria (i.e., miscarriage or termination), the SAE reporting process needs to be followed and the timelines associated with a SAE should be followed.

Causality assessments

Probable

All of the following apply:

- Reasonable association in time between the administration of the study drug and onset and duration of the reported event.
- Description of the clinical phenomenon should be consistent with, or at least plausible, given the known pharmacology and toxicology of the product.
- There should be no other equally plausible explanation(s) of the case. In particular, concurrent use of other products (and possible interactions) or concurrent disease should be taken into account in the assessment.

Possible

- The causality is one (of other) possible and plausible causes for the described event, but the data do not meet the criteria for inclusion in Category A.

Unknown

- An association with the study drug cannot be discounted, but other factors prevent a conclusion from being drawn.

Unlikely

- Sufficient information exists to establish beyond reasonable doubt that the product was not likely to be the cause of the event.

Classification of adverse events

At the conclusion of the study, Medicinal Dictionary for Drug Regulatory Authorities (MeDDRA) terms will be assigned to all adverse events and will be included in the final study report.

Stopping Criteria

If more than 5 patients report a greater than moderate local side effect (irritation, worsening of rash, vesicles/bulla etc) or if the clinical dermatological score in the treatment area as assessed by the clinician has worsened by more than 50% from baseline in more than 5 patients, then all patients will stop medication until further review and changes made to the protocol. If any unanticipated serious adverse effects are noted all subjects will be notified and changes will be made to future protocols and submitted for approval.

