 - change in the expression of selected biomarkers in skin samples obtained from tape stripping (d-squame) at baseline and end of treatment (week 12)
 - change in microbiome at baseline and end of treatment (week 12)

Treatment groups and Duration:

Will enroll up to 25 subjects with CHD; investigational drug will be applied twice a day for 12 weeks by the subjects. Subjects will be asked to come back for a safety follow up visit every 4 weeks until end of treatment.

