Subjects will apply topical Ruxolitinib 1.5% cream twice a day for 12 weeks on eczematous areas of hands and adjoining clinically normal (perilesional) area. We included non-lesional/perilesional skin to evaluate the safety (e.g. irritant or toxic effects) of the compound on irritated/atopic skin, as those subjects have a lower irritancy threshold^{vi}. Also, skin barrier impairment (e.g. increase water loss/TEWL) can be already detected in normal appearing skin in atopic subjects and it is thought to allow penetration of haptens/allergens/irritants with consequent activation of an inflammatory response. It is our hypothesis that treatment with topical Ruxolitinib, a JAK1/JAK2 inhibitor, will normalize skin barrier integrity in perilesion skin. During the study, subjects will be allowed to stay on bland moisturizer and anti-histamine on a stabilized dose and expected to maintain this dose throughout the study. **In addition to clinical and safety outcomes**, the study design will include **exploratory** mechanistic outcomes, in a stepwise tactic. During the trial we will collect: 1) non-invasive skin barrier assessment (i.e. TEWL, SC integrity score); 2) stratum corneum extract to investigate potential biomarkers and skin microbiome (stored for future investigation); 3) Patient oriented outcomes. If the data gathered from the clinical trial demonstrates the clinical improvement we expect, the mechanistic studies will be extremely relevant to start clarifying specific target downstream to Ruxolitinib efficacy in CHD as well as biomarkers that could eventually be investigated in consequent larger clinical trials.

ADMINISTRATIVE ORGANIZATION

UR Dermatology at College Town is the only participating site in this research study.

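### The contraception period of 30 days after stopping drug is given as 112 days, but on the nominal schedule it ends on day 114

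*Combined protocol and SAP*

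**What the plan says.** Section 4 (Study Treatment & Design), Visit 1 item 5, sets the contraception requirement for women of childbearing potential. Birth control is to be used throughout treatment, "including 30 days after stopping study drug (16 weeks or 112 days".

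The visit list at the start of the same section fixes the dates that this depends on:

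- Start of treatment: "visit 1 - (V1, day 0), start of active treatment".
- End of treatment: "visit 4 – 84 +/- 3 days (12 weeks) end of treatment".
- Follow-up: "visit 5 – 112 +/- 3 days (16 weeks) safety follow up 4 weeks post treatment".

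The treatment length is the same in Section 1 ("investigational drug will be applied twice a day for 12 weeks by the subjects") and in Section 2, Design & Methodology ("Subjects will apply topical Ruxolitinib 1.5% cream twice a day for 12 weeks").

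The Reproductive Risks paragraph of Section 5 repeats that women will be counselled on birth control but gives no duration. Item 5 is therefore the only place in the available text that says how long contraception must last.

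**The concern.** The parenthesis cannot describe the 30 days alone, since 112 days is far longer. It can only be the whole period from first application to the end of the 30 days. Read that way, it should equal the treatment length plus 30 days, and it does not. It equals the treatment length plus 28 days, which is the nominal day of Visit 5. The likely explanation is that the Visit 5 date was carried over and 30 days was treated as 4 weeks.

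The instruction is used at Visit 1, before anyone knows when the participant will actually stop. A count from day 0 is then the easy figure to give, and it coincides with the last scheduled visit. Staff or participants who work from it would end contraception slightly earlier than the same sentence requires.

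**Working it through.** **Inputs, all from Section 4**

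- First application: day 0 (Visit 1).
- End of treatment: day 84 nominal, with a window of 84 − 3 = 81 to 84 + 3 = 87 (Visit 4).
- Required cover after stopping: 30 days (Visit 1 item 5).
- Stated total: 16 weeks or 112 days (Visit 1 item 5).

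**Reproducing the stated figure**

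- 16 weeks × 7 = 112 days, so the two numbers inside the parenthesis agree with each other.
- 12 weeks × 7 = 84 days, and 84 + 28 = 112. The stated total follows if the post-treatment period is 4 weeks.
- With the required 30 days, 84 + 30 = 114. The stated total does not follow from the stated rule on the nominal schedule.
- Put the other way, stopping contraception on day 112 after a last application on day 84 leaves 112 − 84 = 28 days of cover.

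**Dependence on the last application day**

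Let L be the day of the last application. The required period ends on day L + 30, and the shortfall of the stated count is L + 30 − 112.

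| Last application (L) | Reading | Period ends (L + 30) | Shortfall of day 112 |
|---|---|---|---|
| 81 | Early edge of Visit 4 window | 111 | None (1 day to spare) |
| 82 | Break-even | 112 | 0 days |
| 83 | 12 weeks counted as days 0 to 83 | 113 | 1 day |
| 84 | Nominal end of treatment | 114 | 2 days |
| 87 | Dosing continued to the late edge of the window | 117 | 5 days |

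Day 112 satisfies the 30-day rule only when L is 82 or less. For someone who stops well before day 82, a fixed count from day 0 errs in the other direction and asks for longer than 30 days.

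**The case against.** The strongest reply is that the sentence already states the correct rule. The 30 days is explicit and runs from stopping the drug, so the parenthesis is only a gloss, and a reader who notices the conflict would follow the rule. That is largely right and is why the point is minor. It does not remove the conflict: the sentence gives two unequal figures, the shorter falls below the stated minimum, and nothing marks it as approximate.

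A second reply is that the gap lies within the schedule's own tolerance, since day 114 falls inside the Visit 5 window of days 109 to 115. That window governs when visits may take place. Item 5 attaches no tolerance to the contraception period, and a late Visit 4 can widen the gap.

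A third reply concerns size. Twelve weeks of dosing from day 0 can fairly be counted as days 0 to 83, which makes the shortfall 1 day, and the 5-day figure needs dosing beyond 12 weeks. Both observations stand. The 5-day case should be read only as an outer bound.

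Finally, the practical consequence is uncertain. Urine pregnancy tests are scheduled at every visit including Visit 5, women who expect to become pregnant during the study are excluded, and pregnancies must be reported to the drug supplier within 24 hours of discovery. Nothing in the documents suggests that a day or two changes the risk with this cream. The consent pages are not available, so the wording given to participants cannot be checked. These points limit the importance of the error but do not correct the day count.

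**Conclusion.** The point holds. The stated total of 112 days does not equal treatment plus 30 days. It is 2 days short if the last application is on day 84 and 1 day short if it is on day 83. There is no shortfall if the last application is on day 82 or earlier, and the shortfall is at most 5 days if dosing continues to a Visit 4 on day 87. The conclusion rests on day 0 being the first day of application, as the visit list states, and on the 30-day wording being the intended rule.

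The error is very small. It touches a safety instruction to staff and leaves endpoints, analyses and sample size unchanged. No harm from the difference is claimed.

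**What to change.** Delete the parenthesis in Section 4, Visit 1 item 5. The remaining sentence is then correct for everyone, including those who stop early.

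If a day count is wanted for counselling, tie it to the last application: birth control until 30 days after the last application of study drug, nominally day 114, and up to day 117 within the Visit 4 window. The period should still be counted from each participant's actual last application.

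The cost is one phrase. No visit or procedure changes, and Visit 5 can stay at day 112.
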